Efferalgan (INN: Paracetamol), syrup for children 30 mg/5 ml ***is prescribed once per set dose only in cases of febrile temperature ($\geq 38.5^{\circ}\text{C}$) presence. The next intake of the product is possible in cases of febrile temperature presence but it may be performed no earlier than at 4-6 hours from the first intake. It is necessary to warn the unnecessary prescription of any antipyretic drug, to exclude its effect on the study results interpretation. The number of antipyretic drug intakes by the patient should be recorded in the primary documentation.***

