Average single dose of the product depends on the child's body weight and is **10-15 mg/kg** of body weight. Maximum daily dose shall not exceed **60 mg/kg** of body weight. Minimum interval between doses of the product shall be 4 hours. For convenience and accuracy of dosing, it is necessary to use a measuring spoon.

On the measuring spoon there are graduations indicating the child's body weight: 4, 6, 8, 10, 12, 14 or 16 kg. Unmarked graduations correspond to intermediate body weight: 5, 7, 9, 11, 13 or 15 kg.

The product can be given to the child both without dilution, and after dilution (with water, milk or juice).

Duration of treatment with Efferalgan®:

3 days as an anti-febrile agent. The product is prescribed only in the case of body temperature rise up to 38.5 °C and above.

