9.2 Diagnostic Scales and Patient's Diary

During the study, the patient's condition and the therapy efficacy will be evaluated using the following parameters: 1) "Symptom Assessment Scale" (Appendix 1) - completed by the physician, 2) IMOS scale completed by the physician (Appendix 2) and also by the parent / adoptive parent (Appendix 3).

Symptom Assessment Scale completion will be conducted on Visit 0, Visit 1, Visit 2 and Visit 3. Also, on Day 5 of therapy, in the patient's diary the Symptom Assessment Scale shall be filled in; this procedure will be performed by the parent/adoptive parent. IMOS scale completion (Appendix 3) and assessment of the ongoing therapy efficacy by the patient's parent/adoptive patient (excellent, good, satisfactory, not efficient) will be held on Visit 3.

In addition, parents / adoptive parents of patients will be given a diary to record the patient's body temperature (twice a day: morning and evening), the time of taking the study product / placebo, the time and amount of taking antipyretic (paracetamol) and other drugs and their dosage and method of taking patients' complaints.

The diary and the diagnostic scales completed by the physician are the primary documentation; upon completion of the examination by the patients, they should be collected and kept together with the patient's medical record. When using electronic diaries, the data downloaded from them will be stored in the Investigator's file.

When conducting Visit 1 procedures, the Investigator must train the parents / adoptive parent to fill out a diary. At each visit, the Investigator must verify the correctness and timeliness of filling the diary with the patient's parent / adoptive parent.

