10. EFFICACY ASSESSMENT

In this study, the efficacy will be assessed based on the body temperature changes recorded in the patient's diaries at home by the parent / adoptive parent of the child; based on the Symptom Assessment Scale, IMOS scale, evaluation of the efficacy of the patient's parent / adoptive therapy, the number of cases of consumption of the antipyretic drug, the number of cases of dropout of patients due to the need to prescribe antibacterial drugs.

The multiplicity and rules for the use of these diagnostic scales are described in detail in the protocol section 9.2 "Diagnostic scales and Patient's diary".

Primary efficacy criterion:

- Fever duration period³ $\delta = -0.52$ days will be considered as a superiority cut-off level. Axillary body temperature level ≤ 36.9 °C confirmed by two consecutive measurements (morning-evening/evening-morning) will be considered as the end of fever.

Secondary efficacy criteria:

- The dynamics of intoxication symptoms by Days 3, 8 of treatment, assessed according to the Symptom Assessment Scale .
- Assessment of the ongoing therapy efficacy by a physician at the end of treatment course (IMOS scale) - complete recovery (0 points), significant improvement (1 point), minor to moderate improvement (2 points), unchanged (3 points), worsening (4 points).
- Assessment of the ongoing therapy efficacy by the patient's parent/adoptive patient (excellent, good, satisfactory, not efficient) - scores from 0 to 3.
- Number of cases of the antipyretic product (paracetamol) consumption for the entire study period.
- Number of patients' dropout patients due to the need to prescribe the antibacterial products.
- Number of patients (%) with body temperature normalization (presence of axillary body temperature ≤ 36.9 °C in two consecutive measurements (morning-evening/evening-morning) on Day 5 of therapy.
- Number of patients (%) with clinical pattern normalization on Day 5 of therapy according to the Symptom Assessment Scale (total ≤ 3 points).

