11. SAFETY ASSESSMENT

The safety of compared drugs will be assessed throughout the study on the occurrence and development of adverse events (AE) recorded primarily on the complaints of patients, as well as on the data of physical examination and the results of laboratory and instrumental examination.

Adverse event - any medically unfavorable event observed in the subject of the study after the use of the medicinal product, which may not have a causal relation with its use.

³ Axillary body temperature > 37.0 °C confirmed by two measurements (morning-evening/evening-morning)

Thus, an adverse event (AE) can be any unfavorable symptom (including deviation of the laboratory value from the norm), a complaint or a disease, the time of occurrence of which does not exclude a causal relationship with the use of the medicinal (test) product, regardless of the presence or absence of such communication.

The severity of AE is established in accordance with the following classification:

- Grade 1 (mild AE): an adverse event easily tolerated by the patient, causing minimal discomfort and not interfering with daily activities;
- Grade 2 (moderate AE): an adverse event that causes discomfort that interferes with daily activities;
- Grade 3 (severe AE): an adverse event that interferes with normal daily activities.

The AE relation to the product prescription is determined by the WHO scale:

Certain. Clinical manifestation of AEs, laboratory findings deviations occur during the period of administration of the product are unlikely to be explained by the presence of existing diseases and other factors. Manifestations of AEs regress after the product discontinuation and occur again after repeated administration.

Probable. Clinical manifestations of AEs, laboratory findings deviations have temporal association with the product administration, are unlikely to have any association with concurrent diseases or other factors, and which regress upon cancellation of the product. Response to the drug re-challenge is unknown.

Possible. Clinical manifestation of AEs, changes in laboratory findings have temporal association with the product administration, but they can be explained by the presence of concomitant diseases or administration of other medicinal products and the influence of chemical compounds. Information on drug withdrawal response is unclear.

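### The end-of-fever rule can declare fever over although the diary records a paracetamol dose, or a reading of 38.5 °C or more, between the two confirming readings

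*Combined protocol and SAP*

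**What the plan says.** Protocol section 10, in line with the synopsis and section 7.1, makes fever duration the primary criterion. A temperature of at most 36.9 °C "confirmed by two consecutive measurements (morning-evening/evening-morning) will be considered as the end of fever". A footnote to the criterion defines fever itself: "Axillary body temperature > 37.0 °C confirmed by two measurements (morning-evening/evening-morning". Neither definition mentions antipyretics.

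The readings come from the parents, who get "a diary to record the patient's body temperature (twice a day: morning and evening" (section 9.2). The same diary takes "the time and amount of taking antipyretic (paracetamol".

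On paracetamol, section 7.4 says "The product is prescribed only in the case of body temperature rise up to 38.5 °C and above" and "Minimum interval between doses of the product shall be 4 hours". It gives 3 days as the duration of antipyretic treatment. Sections 5.5 and 9.3.2 call 38.5 °C and above febrile and put the earliest repeat dose at 4 to 6 hours. Section 5.5 also asks that unnecessary antipyretic prescribing be warned against, "to exclude its effect on the study results interpretation". Paracetamol enters the analysis only as a separate secondary endpoint, the number of uses.

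**The concern.** The second reading is there to confirm that fever has ended. With two scheduled readings a day, a temperature of 38.5 °C or more and a paracetamol dose can both fall between them, and the second reading can then be low because of the dose. A dose given according to the protocol is itself a record that the child was febrile at that moment. The rule ignores this record and can close the fever period before a documented febrile episode.

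The recorded duration would then be too short for that child. If this happens at different rates in the two arms, it moves the primary comparison, for which the plan allows little room. The secondary endpoint of temperature normalisation on Day 5 uses the same two-reading rule.

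**Working it through.** **1. The rule applied to one child.** Every step below is allowed by the text.

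- Morning diary reading: 36.9 °C or lower.
- Between the scheduled readings: 38.5 °C or higher, so paracetamol is permitted and its time goes into the diary.
- Evening diary reading: 36.9 °C or lower.

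Morning and evening form a consecutive pair, so the end of fever is confirmed. The text does not say whether the end is dated to the first or the second reading. Either way, this pair closes the fever period.

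**2. Search for a rule that cancels it.** Sections 9.2 and 9.3 (diary, concomitant therapy), 10 (endpoints), 12.3 (efficacy analysis), 12.6 (missing data) and 12.8 (analysis populations) contain none. No section requires a paracetamol-free interval before a qualifying reading, says that an intervening dose or high reading breaks the pair, or plans a sensitivity analysis. Permitted therapy includes paracetamol, so these children are not removed as protocol deviators.

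**3. The plan's own sample size, for scale.** Inputs from section 12.1: Zα = 1.645, Zβ = 0.842, SD = 0.2 day, means 2.6 and 3.2 days, δ = −0.52 day.

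- Planned difference: 2.6 − 3.2 = −0.60 day. Distance beyond the limit: 0.60 − 0.52 = 0.08 day.
- n = (1.645 + 0.842)² × 2 × 0.2² / 0.08² = 77.3, so 78 per group. The stated figure reproduces.
- Standard error with 78 per group: 0.2 × √(2/78) = 0.032 day. Power at Zα = 1.645: Φ(0.08/0.032 − 1.645) = 80%.

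**4. Illustration with assumed rates.** The documents give no paracetamol use by arm. Assume that the end of fever is called one reading (0.5 day) too early in a share x more of one arm than of the other. The expected difference then moves by 0.5x day.

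- x = 5 points: shift 0.025 day. Excess in placebo gives −0.575 (distance 0.055, power 53%). Excess in the active arm gives −0.625.
- x = 10 points: shift 0.05 day. Excess in placebo gives −0.55 (distance 0.03, power 24%). Excess in the active arm gives −0.65.
- x = 16 points in placebo: shift 0.08 day, which uses up the whole distance.

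The power figures take the plan's SD of 0.2 day and Zα = 1.645 as given. The rates are assumptions, not estimates.

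**The case against.** The strongest reply is that counting readings whatever permitted antipyretic was taken is a coherent choice. Paracetamol is authorised background therapy and is analysed separately, and the footnote requires two measurements for fever, so a single spike is not confirmed fever. That is a fair defence of readings taken under paracetamol in general. It does not cover a febrile episode between the two confirming readings, because the pair is supposed to show that fever was over.

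One can also say that the reading which triggered the dose breaks the sequence, so that morning and evening are no longer consecutive. The text names the pair as morning-evening or evening-morning, and a program working from the scheduled diary readings would accept it.

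Several objections stand in part:

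- The pattern may be uncommon. Section 5.8 describes ARVI temperature as often 37.5–38.0 °C, and section 8.2 excludes children with a positive influenza test.
- One dose is unlikely to suppress two readings 12 hours apart, given a re-dosing interval of 4 to 6 hours. But only the second reading has to be lowered; the first may be a natural low.
- Parents may dose below the trigger, so a dose is strong but not perfect evidence of 38.5 °C.
- Section 12 defers detailed methods to a later analysis plan. A primary endpoint definition should not wait for it.

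A reader might infer that the primary definition needs a 6-hour paracetamol-free window before the first reading. The documents do not support that: 4 to 6 hours is a re-dosing interval, not a stated duration of effect. A reader might also infer that the Day 5 endpoint is seriously affected. Section 7.4 limits antipyretic treatment to 3 days and section 9.1.2 sizes the supply for 3 days, so the effect on Day 5 is probably small.

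**Conclusion.** The point holds as a gap in the endpoint definition. The rule is complete enough to program, and programmed as written it can end fever across an interval that the trial's own diary marks as febrile. It should be corrected before unblinding.

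Its size is unknown. The 0.025 and 0.05 day shifts rest on assumed imbalances of 5 and 10 percentage points and on errors of half a day. They look large mainly because the limit was set at the upper confidence limit of the earlier study, which leaves 0.08 day.

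A reader might infer that the error must work against the product, because placebo children would need more paracetamol. The documents do not establish this. They give no use by arm, and section 5.2.1 lists possible temperature elevation as a side effect of the product, so more doses in the active arm cannot be ruled out. The error could therefore weaken a true effect or enlarge an apparent one.

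**What to change.** In the synopsis and in sections 7.1 and 10, add that a pair of readings does not confirm the end of fever if the diary records a paracetamol dose or a temperature of 38.5 °C or more between them, and that the next qualifying pair is used. Score the temperature-normalisation endpoint the same way. This works whichever reading of the pair dates the end of fever.

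Prespecify two sensitivity analyses:

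- the unrestricted definition as it stands now;
- a version that also disregards readings taken within a stated window after a dose, for example 6 hours.

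The cost is one sentence in three places and two extra runs of the primary analysis. No new data are needed: section 9.2 already collects dose times, and section 7.8 treats the diary as primary data to be transferred to the case report form. The downside is that a dose given below the 38.5 °C trigger would delay the recorded end of fever for that child; the unrestricted analysis shows how much this matters. The change concerns only how readings are scored, not antipyretic treatment.

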11. SAFETY ASSESSMENT

The safety of compared drugs will be assessed throughout the study on the occurrence and development of adverse events (AE) recorded primarily on the complaints of patients, as well as on the data of physical examination and the results of laboratory and instrumental examination.

Adverse event - any medically unfavorable event observed in the subject of the study after the use of the medicinal product, which may not have a causal relation with its use.

³ Axillary body temperature > 37.0 °C confirmed by two measurements (morning-evening/evening-morning)

Thus, an adverse event (AE) can be any unfavorable symptom (including deviation of the laboratory value from the norm), a complaint or a disease, the time of occurrence of which does not exclude a causal relationship with the use of the medicinal (test) product, regardless of the presence or absence of such communication.

The severity of AE is established in accordance with the following classification:

- Grade 1 (mild AE): an adverse event easily tolerated by the patient, causing minimal discomfort and not interfering with daily activities;
- Grade 2 (moderate AE): an adverse event that causes discomfort that interferes with daily activities;
- Grade 3 (severe AE): an adverse event that interferes with normal daily activities.

The AE relation to the product prescription is determined by the WHO scale:

Certain. Clinical manifestation of AEs, laboratory findings deviations occur during the period of administration of the product are unlikely to be explained by the presence of existing diseases and other factors. Manifestations of AEs regress after the product discontinuation and occur again after repeated administration.

Probable. Clinical manifestations of AEs, laboratory findings deviations have temporal association with the product administration, are unlikely to have any association with concurrent diseases or other factors, and which regress upon cancellation of the product. Response to the drug re-challenge is unknown.

Possible. Clinical manifestation of AEs, changes in laboratory findings have temporal association with the product administration, but they can be explained by the presence of concomitant diseases or administration of other medicinal products and the influence of chemical compounds. Information on drug withdrawal response is unclear.

Questionable. Clinical manifestation of AEs, changes in laboratory findings manifest without a clear temporal association with the product administration; other factors are present (medicinal products, diseases, chemical compounds, medical manipulations), which may have caused them.

Unlikely. Clinical manifestation of AEs, abnormal laboratory findings related to AEs, are hard to assess. Necessary additional data for the assessment, or the same date are presently analyzed.

Unclassified. Reports on suspected AEs cannot be assessed as there are no enough data or data are contradictory.

In the event of occurrence of AE, the study physician should take and record their actions in primary and secondary documentation, for example, prescribe additional medications (which, in what dose, for what period), hospitalize the patient (if necessary), etc.

Adverse reaction (AR) - regarding the pre-registration clinical use of a new medicinal product or its use for new indications, especially if the therapeutic doses have not been precisely established, - all the negative reactions associated with the use of any dose of the medicinal product. The term "associated with the use of a medicinal product" means that there is at least a minimal possibility of a causal link between the medicinal product and an undesirable phenomenon, i.e. relationship can not be ruled out.

For registered medicinal products, this term means all the negative reactions associated with the use of the medicinal product in the usual doses used for the prevention, diagnosis or treatment of diseases, as well as for changes in physiological functions.

Unforeseen adverse reaction - an undesirable reaction, the nature or severity of which is inconsistent with known information about the product (for example, with a Investigator's brochure for an unregistered study project)

Investigators must document in the primary documentation and individual registration cards all adverse events that occurred with the patient during the study and / or caused the suspension of the study medication. The patient should be warned that during the break between study visits, he/she should inform the physician about any new symptoms that appear.

All adverse events that occurred during the study (start, duration, ending, description, intensity, outcome), as well as measures for their relief, are recorded in the CRF. In the event of serious adverse events (SAEs), it is necessary to inform representatives of the study sponsor / representatives of the contract study organization within 24 hours.

Any adverse medical event that meets the definition of AE, which, moreover, at any dose, will be considered a serious AE (SAE):

- leads to death;
- poses a threat to life;
- leads to persistent or significant disability or incapacity;
- leads to inpatient hospitalization or extension of current hospitalization;
- represents a congenital anomaly or birth defect;

- any adverse medical event that may not immediately threaten the life and lead to death or hospitalization, but from a medical and scientific point of view may pose a threat to the patient or require the intervention to prevent any of the above outcomes.

These events are usually considered serious.

Attention: the term "life-threatening" refers to an adverse event in which there is a risk of patient's death due to this reaction at the time of adverse event. This does not apply to any event that would hypothetically lead to death, if it would be more serious.

Analysis of safety parameters is based on the following data:

- frequency of occurrence and development of adverse events (AEs) recorded, according to the data of spontaneous patients' reports, clinically significant changes in vital signs (HR, RR) and clinically significant deviations of laboratory test indicators and instrumental methods of examination from baseline values;
- overall assessment of the tolerability of study products by the patient's parent/ adoptive parent and the Investigator.

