7. STUDY DESIGN

7.1 Parameters evaluated during the study

This study assesses the efficacy and safety of nasal and sublingual spray Polyoxidonium[®] (active ingredient of Azoximer bromide) compared with placebo, as part of complex therapy for ARVI not requiring hospitalization in children aged 1–12 years.

Primary efficacy criterion:

- Fever duration period² $\delta = -0.52$ days will be considered as a superiority cut-off level. Axillary body temperature level ≤ 36.9 °C confirmed by two consecutive measurements (morning-evening/evening-morning) will be considered as the end of fever.

Secondary efficacy criteria:

- The dynamics of intoxication symptoms by Days 3, 8 of treatment, assessed according to the Symptom Assessment Scale.
- Assessment of the ongoing therapy efficacy by a physician at the end of treatment course (IMOS scale) - complete recovery (0 points), significant improvement (1 point), minor to moderate improvement (2 points), unchanged (3 points), worsening (4 points).
- Assessment of the ongoing therapy efficacy by the patient's parent/adoptive patient (IMOS scale) - excellent, good, satisfactory, not efficient - scores from 0 to 3.
- Number of cases of the antipyretic product (paracetamol) consumption for the entire study period.
- Number of patients' dropout patients due to the need to prescribe the antibacterial products.
- Number of patients (%) with body temperature normalization (presence of axillary body temperature ≤ 36.9 °C in two consecutive measurements (morning-evening/evening-morning) on Day 5 of therapy.
- Number of patients (%) with clinical pattern normalization on Day 5 of therapy according to the Symptom Assessment Scale (total ≤ 3 points)

Safety endpoints

Safety and tolerability assessments will be conducted throughout the entire study (from the moment of the first use of the study product/ placebo) on the following parameters:

² Axillary body temperature > 37.0 °C confirmed by two measurements (morning-evening/evening-morning)

- frequency of AEs occurrence recorded according to the data of spontaneous patients' reports, presence of complaints, and also to physical examination data, clinically significant deviations of laboratory and instrumental methods of examination from baseline values;

Conclusion on safety of the study product will be made after a statistical assessment of all AEs, including serious ones, which identified at least possible relation to the study product.

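### The causality category called Unlikely is defined as awaiting data, so an event still pending at database lock can fall outside the safety conclusion; separately, every Grade 2 AE also meets the Grade 3 wording

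*Combined protocol and SAP*

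**What the plan says.** **Causality.** Section 11 lists six categories: Certain, Probable, Possible, Questionable, Unlikely and Unclassified. Three matter here:

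- "Questionable. Clinical manifestation of AEs, changes in laboratory findings manifest without a clear temporal association with the product administration", with other factors present that may explain the event.
- "Unlikely. Clinical manifestation of AEs, abnormal laboratory findings related to AEs, are hard to assess". The definition continues: "Necessary additional data for the assessment, or the same date are presently analyzed".
- The last category on the list is worded "Unclassified. Reports on suspected AEs cannot be assessed as there are no enough data or data are contradictory".

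The same section defines an adverse reaction for a product not yet registered. An event counts as associated with the product if there is even a minimal possibility of a causal link, so that a relationship cannot be excluded.

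**Conclusion.** Section 7.1 (safety endpoints) says the conclusion on safety follows a statistical assessment of AEs "which identified at least possible relation to the study product". The synopsis row on safety assessment criteria has the same sentence.

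**Severity.** The middle grade is worded "Grade 2 (moderate AE): an adverse event that causes discomfort that interferes with daily activities", while the top grade is worded "Grade 3 (severe AE): an adverse event that interferes with normal daily activities".

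**Analysis.** Section 12.2 plans AE summaries by treatment group, with further breakdowns by severity and by relation to the product. Section 12.4 presents all AEs and SAEs descriptively and compares AE incidence between groups by Fisher's exact test.

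**The concern.** A causality scale works only if each label and its definition point the same way. Here an investigator with an unresolved event who follows the definition must choose *Unlikely*. Anyone who later reads the code sees a judgement against a causal link that nobody made. The conclusion rule then selects on that code, so an unanswered question can be handled as a negative answer.

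The mismatch also works in the other direction. An investigator who follows the word will use *Unlikely* for a doubtful link, which the written scale assigns to *Questionable*. The synopsis names 13 sites, and they can code the same event differently while each has a reason to think the scale was followed.

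The severity grades raise a similar problem. If the wording lets a moderate event be graded severe, the severity breakdown reflects the grader's habit as well as the event.

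**Working it through.** The plan gives no figure to reproduce. The check sets the definitions against the rules that use them.

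**Step 1. Causality categories against the conclusion rule.**

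| Category | What its definition rests on | At least possible? |
|---|---|---|
| Certain | Timing fits, other causes improbable, event recurs on re-exposure | Yes |
| Probable | Timing fits, other causes improbable, event regresses on withdrawal | Yes |
| Possible | Timing fits, other causes could explain it | Yes |
| Questionable | Timing unclear, other causes present | No |
| Unlikely | Hard to assess, data needed or under analysis | No |
| Unclassified | Too few data, or contradictory data | No |

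Three of six categories pass the rule and three do not. Of the three that do not, two (Unlikely and Unclassified) are defined by the state of the data. Only Questionable rests on evidence against a link.

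**Step 2. The conclusion rule against the adverse-reaction definition.** A pending event has, by definition, a relationship that has not been excluded. Under the adverse-reaction paragraph of Section 11 it is associated with the product. Under Section 7.1 and the synopsis it is outside the conclusion. No passage says which prevails.

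**Step 3. Can an event still be pending at lock?** Section 11.1 requires significant laboratory deviations at Visit 3 (Day 8 ± 1) to be followed until they normalise or the cause is found. The only later scheduled contact is Visit 4 (Day 12 ± 1), a telephone call with no laboratory test (Section 9.1.5, Appendix 5). Follow-up beyond that is required for AEs (Section 11.2). No section requires the causality code to be revisited and made final before the database closes. A pending code at lock is therefore possible; how often it would occur cannot be derived.

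**Step 4. Scale of one event.** The planned number randomised is 86 per group. One child moved in or out of the related-AE count changes that group's rate by 1/86 = 1.2 percentage points; five children would change it by 5/86 = 5.8 points. The one-to-five range is an assumption chosen only to show scale. It supposes that each child has no other AE rated at least possible and that all 86 are in the safety population.

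**Step 5. Severity.** Write D for discomfort and I for interference with daily life.

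- Grade 2 requires D and I.
- Grade 3 requires I.
- D and I together imply I, so every Grade 2 event meets Grade 3.
- I alone does not imply D, so a Grade 3 event need not meet Grade 2.

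The overlap runs one way. What separates the grades on paper is whether discomfort is required. Grade 3 states no greater degree of interference.

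**Step 6. What does not depend on either scale.** The all-AE and SAE presentations and the Fisher comparison (Section 12.4) use no causality filter. Seriousness has its own criteria in Section 11, so SAE identification and the 24-hour report do not depend on the severity grade.

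**The case against.** The strongest reply is that pending is a temporary status. AEs are followed until they resolve or stabilise (Section 11.2), laboratory deviations until they normalise or are explained (Section 11.1), and missing or inconsistent data are queried before the database closes (Section 16.3). Most pending events may well be settled by then. This stands as a limit on size, but it does not supply the missing rule. Follow-up to stabilisation settles the clinical course and does not by itself settle causality. An entry of *Unlikely* is a completed field, so a check for missing data need not flag it.

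A second reply is that one sentence is being read as the whole safety basis. Section 7.1 also names the frequency of AEs with no causality filter, Section 11 lists broader safety data, and Section 12.4 analyses all AEs. This also stands: the information will be reported. But the one sentence that says what the conclusion is drawn from restricts it to events with at least a possible relation.

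A third is that the text is a rough translation and both defects may be slips. That is plausible, but it is the text investigators will apply.

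A reader might infer more than the documents support:

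- *That AEs are misclassified.* The documents show wording that permits it; they contain no coded events.
- *That the treatment comparison is biased.* Section 7.3.1 keeps product codes from investigators until database lock, with disclosure only for product-related AEs. Nothing suggests that the scale would be applied differently by arm.
- *That Grades 2 and 3 are identical.* Step 5 shows a one-way overlap, and the labels moderate and severe still convey an order.

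**Conclusion.** The point holds as a defect in operative wording. As written, an event still pending at database lock can be filed as *Unlikely* and left out of the stated safety conclusion, in conflict with the adverse-reaction definition in the same section. Independently, the severity breakdown in Section 12.2 cannot reliably separate moderate from severe AEs.

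The size cannot be stated, because the number of pending events is not in the documents; the percentages in the working show scale only. The effect is confined to the relatedness and severity summaries and to the conclusion rule. The conclusion rests on two readings: that *at least possible* means Certain, Probable or Possible, and that no separate instruction outside these documents tells sites how to code or finalise pending events.

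**What to change.** 1. **Section 11, causality.** Make label and definition agree. Give *Unlikely* the weak-link definition now under *Questionable*, and move the awaiting-data definition to a separately named pending category.
2. **Pending and unclassified events.** Require pending causality assessments to be resolved before database lock. State how any that remain pending or unclassified are handled, consistently with the adverse-reaction definition. One option is a sensitivity count that treats them as related; the documents do not dictate a particular convention.
3. **Section 7.1 and the synopsis row on safety assessment criteria.** In both places, base the safety conclusion on all treatment-emergent AEs by arm, with related AEs as a subset. Changing only one would create a new contradiction.
4. **Section 11, severity.** Give Grade 3 a criterion distinct from Grade 2, for example that the event prevents normal daily activities.

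The cost is wording, matching changes to the CRF code list and a short note to sites. No visit, test or sample size changes, and the all-AE analysis is already planned in Sections 12.2 and 12.4. The one small downside is that the related-AE count may be slightly higher.
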